# 6.3 Subject Exclusion Criteria

- a) Patients who have a standard curative option for their lymphoid malignancy at current state of disease are excluded. For eligibility on this trial, allogeneic stem cell transplantation is not to be considered a standard curative option.
- b) Any serious medical condition, laboratory abnormality, or psychiatric illness that would prevent the subject from signing the informed consent form.
- c) Pregnant females. (Lactating females must agree not to breast feed while taking carfilzomib, lenalidomide or romidepsin).
- d) Known hypersensitivity to thalidomide.
- e) The development of erythema multiforme if characterized by a desquamating rash while taking thalidomide or similar drugs.
- f) Prior use of lenalidomide if discontinued due to toxicity.
- g) Prior therapy with romidepsin if discontinued due to toxicity.
- h) Prior therapy with carfilzomib if discontinued due to toxicity.
- i) Prior therapy with a proteasome inhibitor if discontinued due to toxicity.
- j) Concurrent use of other anti-cancer agents or treatments.
- k) Known seropositive and requiring anti-viral therapy for human immunodeficiency virus (HIV), hepatitis B virus (HBV) or hepatitis C virus (HCV).

- I) Concurrent malignancy requiring active therapy.
  - Patients with more than one type of lymphoma may be enrolled after discussion with the MSK Principal Investigator.
- m) Known central nervous system or meningeal involvement (in the absence of symptoms investigation into central nervous system involvement is not required).
- n) The following known cardiac abnormalities:
  - 1. Congenital long QT syndrome.
  - QTc/QTf interval ≥ 480 milliseconds; unless secondary to pacemaker or bundle branch block.
  - 3. Myocardial infarction within 6 months of cycle one, day one (C1D1). Subjects with a history of myocardial infarction between 6 and 12 months prior to C1D1 who are asymptomatic and have had a negative cardiac risk assessment (treadmill stress test, nuclear medicine stress test, or stress echocardiogram) since the event may participate.
  - 4. Other significant ECG abnormalities including 2nd degree atrioventricular (AV) block type II, 3rd degree AV block.
  - 5. Symptomatic coronary artery disease (CAD), e.g., angina Canadian Class II-IV (see Appendix B). In any patient in whom there is doubt, the patient should have a stress imaging study and, if abnormal, angiography to define whether or not CAD is present.
  - 6. An ECG recorded at screening showing evidence of cardiac ischemia (ST depression of ≥2 mm, measured from isoelectric line to the ST segment). If in any doubt, the patient should have a stress imaging study and, if abnormal, angiography to define whether or not CAD is present.
  - 7. Congestive heart failure (CHF) that meets New York Heart Association (NYHA) Class II to IV definitions (see Appendix C) and/or ejection fraction <45% by echocardiogram, or cardiac MRI.
  - 8. A known history of sustained ventricular tachycardia (VT), ventricular fibrillation (VF), Torsade de Pointes, or cardiac arrest unless currently addressed with an automatic implantable cardioverter defibrillator (AICD).
  - 9. Hypertrophic cardiomegaly or restrictive cardiomyopathy from prior treatment or other causes.
  - 10. Uncontrolled hypertension, i.e., blood pressure (BP) of ≥170/95; patients who have a history of hypertension controlled by medication must be on a stable dose (for at least one month) and meet all other inclusion criteria.
  - 11. Any cardiac arrhythmia requiring an anti-arrhythmic medication (excluding stable doses of beta-blockers)

- 12. Patients taking drugs that can cause significant QTc/QTf prolongation, unless able to be switched to non-QTc/QTf prolonging medication or on a stable dose without significant QT prolongation (>470 msec)
- 13. Concomitant use of significant CYP3A4 inhibitors unless able to be switched to a non-CYP3A4 inhibiting medication..
  - Caution should be used when administering study drugs to
    patients taking medications significantly metabolized by these
    enzymes refer to (http://medicine.iupui.edu/clinpharm/ddis/clinical-table/) for clinically relevant medications Particular attention
    should be paid to patients receiving warfarin. Patient should have
    coagulation paramaters monitored regularly, and warfarin dose
    adjusted accordingly. If these drugs cannot be discontinued or
    replaced, enrollment may be allowed after discussion with MSK PI.

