# 9.5.1 Prohibited/monitored concurrent therapy

- Any investigational agent other than lenalidomide or romidepsin.
- Any medications at high risk of causing QTc/QTf prolongation or inducing torsades de pointes (as listed in Appendix E).
- Concomitant use of CYP3A4 inhibitors with romidepsin should be avoided (excluding anti-emetics) to prevent potential increase in romidepsin exposure during concomitant treatment with these drugs. Should a patient already enrolled on this study require treatment with a drug listed in Appendix F romidepsin must be interrupted prior to starting these drugs and should not resume until a washout period of at least 5 half-lives has elapsed.

Any medications that have the potential to alter serum electrolytes (e.g., diuretics) should be monitored very closely for electrolyte abnormalities as these can contribute to the risk of QTc/QTf prolongation and ventricular arrhythmias.

Memorial Sloan Kettering Cancer Center IRB Number: 14-179 A(6) Approval date: 12-Dec-2017

Administrative Update 1: 06-Dec-2018

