#### 10.6 Electrocardiograms

An ECG must be performed within 1 hour (after administration of antiemetic premedication) prior to romidepsin and after completion of each romidepsin infusion for cycles 1 and 2. If no QTc/QTf value greater than 480 msec is demonstrated by auto-read or manual read then further ECGs may be omitted for

the duration of study. If a QTc/QTf value greater than 480 but less than 500 msec is encountered then ECGs should be performed within 1 hour prior to romidepsin infusion for the first dose of each subsequent cycle.

If a QTc/QTf is  $\geq$  500 msec is encountered, ECGs should be repeated twice more for a mean of three QTc/QTf values. If the mean is  $\geq$  500 msec, follow dose modification guidelines in **table 6**.

**Note to Investigators:** At the Investigator's discretion, more intensive ECG monitoring can be performed for all romidepsin administrations.

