## **Appendix E – Medications That May Cause QTc Prolongation**

The following table presents a list of drugs that may prolong the QTc. These drugs are prohibited during the study. Romidepsin may be administered after a 5 half-life washout period elapses following the use of these drugs. Washout period is based on roughly 5 half-lives and rounded to a convenient interval. Patients taking lower risk drugs not known to interact with the study drug will be monitored and may be allowed on study.

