## **Medications That May Cause QTc Prolongation**

Compound (Brand Name)	Compound Half-Life	Possible Washout Period (Hours)	Possible Washout Period (Days)
Antiarrhythmics		,	1
Amiodarone (Cordarone, Pacerone)	58 days (15-142) 36 days (active metabolite)		180
Disopyramide (Norpace, Norpace CR)	6.7 hr (4-10)	36	
Dofetilide (Tikosyn)	10 hr	48	
Flecainide (Tambocor)	20 hr (12-27)		5
Ibutilide (Corvert)	6 hr (2-12) (variable among patients)	36	
Procainamide (Pronestyl, Procanbid,	3-4 hr for PA and NAPA (active	24	
Procan)	metabolite)		
Quinidine (Quinaglute, Cardioquin, Quinidex)	6-8 hr in adult; 3-4 hr in children	36	
Sotalol (Betapace, Sorine)	12 hr	72	
Antibiotics			
Azithromycin (Zithromax, Zithromax Tri- Pack, Zithromax Z-Pak, Zmax)	Immediate release: 68-72 hr, extended release 59 hr		12-15
Clarithromycin (Biaxin, Biaxin XL)	Nonlinear PK 3-4 hr (250 mg Q12) 5-7 hr (500 mg Q12)	36	
Erythromycin (Benzamycin, Eyrc, Eglades, Erygel, E-solve 2, Akne-Mycin, Eryderm, Sansac, Erythro-Statin, Erymax, Staticin, T-Stat, C-solve-2, Erycetter, PCE, Ery-Tab, E-Mycin, E-Base, E.E.S., Eryped, E.E.S 200, E.E.S 400, Pediamycin, Eryzole, Erythrocin)			
Gatifloxacin (Tequin, Tequin Teqpaq)	7-14 hr	48	
Grepafloxacin (Raxar) Antibiotics (cont'd)	16 hr		3
Levofloxacin (Levaquin, Quixin, Elequin)	6-8 hr	48	
Moxifloxacin (Avelox, Vigamox)	12 ± 1.3 hr	72	
Sparfloxacin (Zagam)	20 hr (16-30)		4
Telithromycin (Ketex)	2-3 hr	24	
Anticonvulsants			
Felbamate (Felbatol)	20-23 hr		5
Fosphenytoin (Cerebyx)	12-29 hr		6
Antidepressants			•
Venlafaxine (Effexor)	5 ± 2 hr for parent comp. 11± 2 hr for OVD (active metabolite)	60	
Antidiarrheals			
Octreotide (Sandostatin)	1.7 hr	12	
Antiemetics			•
Dolasetron (Anzemet)	8.1 hr		
Droperidol (Inapsin)	2.2 hr	10	
Domperidone (Motilium)	7-8 hr	48	
Palonosetron (Aloxi) Antihypertensives	40 hr	 	10

Compound (Brand Name)	Compound Half-Life	Possible Washout Period (Hours)	Possible Washout Period (Days)
Moexipril/Hydrochlorothiazide (Uniretic)	2-9 hr(include active metabolite) for moexipril; 5.6-14.8 hr for HCTZ	48	
Antimalarials			•
Halofantrine (Halfan)	6-10 days (variable among individuals)		45
Quinidine (Quinaglute, Cardioquin, Quinidex)	6-8 hr in adult; 3-4 hr in children	36	
Antimanics			
Lithium (Eskalith, Lithobid, Lithonate)	24 hr (10-50)		7
Antineoplastics			
Arsenic trioxide (Trisenox)	Not characterized		
Tamoxifen (Nolvadex)	5-7 days (biphasic)		30
Antiprotozoals			
Pentamidine (NebuPent, Pentam)	6.4 ± 1.3 hr	36	

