Antipsychotic agents			
Chlorpromazine (Thorazine)	30 ± 7 hr		7
Haloperidol (Haldol)	18 ± 5 hr		5
Mesoridazine (Serentil)	24-48 hr (animal study)		10
Pimozide (Orap)	55 hr		14
(Continued from previous page)			
Antipsychotic agents (cont'd)			
Quetiapine (Seroquel)	6 hr	36	
Risperidone (Risperdal, Risperdal Consta)	3-20 hr (extensive to poor metabolizer) 9-hydroxyrisperidone (active metabolite) T 1/2 = 21-30 hr (extensive to poor metabolizer)		4
Thioridazine (Mellaril)	20-40 hr (Phenothiazines)		7
Ziprasidone (Geodon, Zeldox)	7 hr	36	
Antispastics			
Tizanidine (Zanaflex)	2.5 hr	12	
Antivirals	-		
Amantadine (Symadine, Symmetrel)	17 ± hr (10-25)		4
Foscarnet (Foscavir)	87.5 ± 41.8 hr (distribution and release from bone)		20
Analgesics			
Levomethadyl (Orlaam)	Multiple compartment PK with active metabolite 2.6 day for LAAM, 2 day for nor-LAAM, 4 day for dinor-LAAM		20
Asthma medications			
Salmeterol (Advair Diskus, Serevent, Serevent Diskus)	5.5 hr (only one datum)	36	
Calcium channel blockers			-
Bepridil (Vascor)	42 hr (26-64)		10
Isradipine (DynaCirc)	8 hr (multiple metabolites)	48	1

Compound (Brand Name)	Possible Washout Period (Hours)	Possible Washout Period (Days)	
Nicardipine (Cardene) Cholinergic enhancers	~2 hr post IV infusion	12	
Cisapride (Propulsid)  Diuretics	6-12 hr, up to 20 hr	60	
Indapamide (Lozol) Immunosuppressants	14 hr (biphasic elimination)		3
Tacrolimus (Prograf, Protopic)  Migraine medications	~34 hr in healthy patients ; ~19 hr in kidney transplant		7
Naratriptan (Amerge)	6 hr	36	1
Sumatriptan (Imitrex)	2.5 hr	12	
Zolmitriptan (Zomig)	2.8-3.7 hr (higher in female)	18	
Narcotic pain relievers	,	1	
Methadone (Dolophine, Methadose)	15-30 hr		7
Sedatives	1		
Chloral hydrate	Readily converted to Trichloroethanol (active metabolite T½= 7-10 hour)	48	

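### Exclusion n, item 12 lets a patient stay on a stable dose of a QTc-prolonging drug, but Section 9.5.1 and Appendix E bar the listed drugs and require a washout before romidepsin

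*Combined protocol and SAP*

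**What the plan says.** Three places in the combined protocol and SAP deal with QTc-prolonging co-medication.

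- **Section 6.3 (Subject Exclusion Criteria), exclusion n, item 12** excludes patients on drugs that can significantly prolong QTc/QTf, "unless able to be switched to non-QTc/QTf prolonging medication or on a stable dose without significant QT prolongation (>470 msec"). There are two ways past the exclusion: switch the drug, or stay on it at a stable dose with a QTc not above 470 msec. Appendix E is not mentioned.
- **Section 9.5.1 (Prohibited/monitored concurrent therapy)** lists "Any medications at high risk of causing QTc/QTf prolongation or inducing torsades de pointes (as listed in Appendix E"). It gives no stable-dose exception for these drugs.
- **Appendix E** says of the drugs in its table: "These drugs are prohibited during the study. Romidepsin may be administered after a 5 half-life washout period elapses following the use of these drugs". It then adds: "Patients taking lower risk drugs not known to interact with the study drug will be monitored and may be allowed on study". It does not say that any drug in the table counts as lower risk.

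The Appendix E table includes drugs often taken long term, among them venlafaxine, quetiapine and methadone.

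On monitoring, Section 10.6 (Electrocardiograms) requires ECGs before and after each romidepsin infusion in cycles 1 and 2. It continues: "If no QTc/QTf value greater than 480 msec is demonstrated by auto-read or manual read then further ECGs may be omitted for" the remainder of the study.

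**The concern.** The stable-dose exception has a purpose only if the patient keeps taking the drug, because replacing it is already the other exception. Item 12 therefore describes an enrolled patient who remains on a QTc-prolonging drug. For a drug in its table, Appendix E does not allow that patient to exist on study.

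Safety and toxicity are the primary endpoint (Section 2.1), and a QTc/QTf of 500 msec or more is treated as an alert linked to romidepsin (the section on romidepsin dose modification for cardiac toxicity). More than one centre recruits (Section 7.0). If screening staff work from item 12 and pharmacy staff from Appendix E, the same patient could be handled differently at different sites. One site would give romidepsin with a barred drug. Another would stop the drug first, or find that it had enrolled someone it could not dose.

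**Working it through.** No arithmetic underlies the conflict itself. It is shown by applying each rule to one patient.

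**Test patient:** on a stable dose of a drug in the Appendix E table, QTc 450 msec, no intention to switch.

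| Rule | Question | Answer for this patient |
|---|---|---|
| Section 6.3, n item 2 | QTc/QTf at or above 480 msec? | No (450), not excluded |
| Section 6.3, n item 12 | Stable dose and QTc not above 470 msec? | Yes (450), not excluded; drug continues; washout 0 |
| Section 9.5.1 | Drug on the Appendix E list? | Yes; no stable-dose exception given |
| Appendix E | Drug in the table? | Yes; barred on study; romidepsin only after 5 half-lives |

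Item 12 and Appendix E give different answers for the same patient.

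**Size of the difference in washout.** Item 12 asks for none under the stable-dose exception. Appendix E applies roughly five half-lives, rounded to a convenient interval. Its tabulated values follow from its own half-lives:

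- Quetiapine: 5 × 6 h = 30 h, listed as 36 h.
- Venlafaxine, by its active metabolite: 5 × 11 h = 55 h, listed as 60 h.
- Methadone, at the upper half-life: 5 × 30 h = 150 h = 6.25 days, listed as 7 days.

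All three fit within the 28-day pretreatment window in Section 8.2. They are examples and do not bound the table. Bepridil (10 days), pimozide (14) and levomethadyl (20) also fit within 28 days, but tamoxifen (30 days) does not.

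**Do other exclusions close the gap?** In part. Item 11 excludes arrhythmias that need an anti-arrhythmic, which covers most patients on the listed antiarrhythmics. Item 13 restricts significant CYP3A4 inhibitors and so reaches drugs such as clarithromycin, which is in both Appendix E and Appendix F. Exclusions j and l bar concurrent anti-cancer agents and malignancy under active therapy, which removes most use of tamoxifen. None of these reaches venlafaxine, quetiapine or methadone.

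**What monitoring remains?** Potassium and magnesium must be at or above the lower limit of normal, or corrected, before romidepsin (Section 9.2). ECGs surround every infusion in cycles 1 and 2. If none exceeds 480 msec, Section 10.6 lets them stop. A patient kept on a listed drug under item 12 could then have no scheduled ECG from cycle 3 onward.

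**The case against.** The best defence is that the rules are cumulative. An exclusion criterion decides who may not enter and does not authorise any drug combination. Section 9.5 (Concomitant Medications) makes drugs for other conditions subject to the restrictions that follow it, and Section 9.5.1 follows directly. On this view the test patient is enrolled, stops the drug, completes the washout and then receives romidepsin, so a site that skipped the washout would simply be deviating.

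A second defence is that the lower-risk sentence in Appendix E reconciles the texts: the stable-dose exception serves unlisted drugs and Appendix E governs listed ones. The heading of Section 9.5.1, which covers monitored as well as prohibited therapy, points the same way.

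These readings are possible, but item 12 states neither. Its exception is written for drugs that can significantly prolong QTc, not for lower-risk ones. The cumulative reading also leaves the exception empty for every listed drug. Section 9.5 separately permits supportive therapy already under way at baseline, which adds to the ambiguity. The heading of Section 9.5.1 softens that section only, since the ban in Appendix E is unqualified.

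Some of the defence does stand. The 470 msec limit in item 12 is tighter than the general 480 msec exclusion. Stopping ECGs after cycle 2 is optional, applies to all patients and is not created by item 12. The study calendar still marks ECGs in later cycles, subject to the ECG section, and investigators may do more. The documents also do not show which of the two rules the sponsor intended.

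**Conclusion.** The concern holds. For a drug in the Appendix E table, item 12 allows a patient to remain on it, while Appendix E bars it and requires a washout before romidepsin. Following item 12 alone leads either to co-administration with a barred drug or to enrolling a patient who cannot be dosed.

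In the three examples the difference is no washout against 36 hours, 60 hours or 7 days. The documents do not give the number of patients on listed drugs, so no count is claimed. Sample size, the stopping rule and error rates are unaffected. The conclusion assumes that the lower-risk sentence refers to drugs outside the table, which is the natural reading because the sentences before it ban those inside. Existing QT safeguards reduce the hazard, but the text should be corrected because a single edit removes the conflict.

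**What to change.** Reword Section 6.3, exclusion n, item 12 along these lines:

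> A patient taking a drug that can significantly prolong QTc/QTf is excluded unless (a) the drug is replaced by one that does not prolong QTc/QTf and, if it is listed in Appendix E, the washout given there is complete before cycle 1 day 1; or (b) the drug is not listed in Appendix E, the dose is stable, and QTc/QTf does not exceed 470 msec.

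Section 9.5.1 and Appendix E can then stay as they are.

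If the sponsor did intend stable listed drugs to continue, the opposite repair is needed: state the exception in Section 9.5.1 and Appendix E, and keep scheduled ECGs beyond cycle 2 for those patients.

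The cost of the recommended change is one amended criterion. Patients who cannot stop a listed drug become ineligible; the documents give no basis for estimating how many. Others wait for the listed washout, which is 36 hours to 7 days in the three examples and longer for some other listed drugs.

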#### 7.0 RECRUITMENT PLAN

Potential research subjects will be identified by a member of the patient"s treatment team, the protocol investigator, or research team. If the investigator is a member of the treatment team, s/he will screen their patient"s medical records for suitable research study participants and discuss the study and their potential for enrolling in the research study. Potential subjects contacted by their treating physician will be referred to the investigator/research staff of the study. Furthermore, eligible patients from the lymphoma or myeloma service will be identified by individual consenting physicians at the time of medical disciplinary rounds or in clinic at Memorial Sloan Kettering Cancer Center or the University of Nebraska Medical Center.

#### 8.1 PRETREATMENT EVALUATION

# 8.2 Documentation of tests resulted and/or verification to be performed within 28 days of starting treatment.

- 1. Record prior medications and treatments
- 2. Record prior anti-cancer therapy
- 3. Physical examination
- 4. ECOG performance status
- 5. 12 lead ECG
- 6. ECHO or Cardiac MRI
- 7. Complete metabolic panel, including magnesium and phosphorus
- 8. Lactate dehydrogenase (LDH)
- 9. PET/CT or CT Chest, Abdomen, and Pelvis
- 10. Register patient with Revlimid REMS® program.

- 11. mSWAT for patient with cutaneous lymphoma.
- 12. Sezary panel in patients with Sezary syndrome only.
  - Sezary panel: peripheral blood flow cytometry including CD2, CD3, CD4, CD8, CD26 and or CD7
- 13. Phase IIa only: patients with suspected or known prior bone marrow involvement must have a bone marrow biopsy performed.
- 14. Pregnancy testing for females of childbearing potential within 10-14 days and again 24 hours prior to prescribing lenalidomide per the Revlimid REMS® program.

# 8.3 Documentation of tests resulted and/or verification to be performed within 14 days of starting treatment.

Complete blood count (CBC)

#### 9.1 TREATMENT/INTERVENTION PLAN

# 9.2 Pretreatment electrolyte assessment and drug management

Prior to initiation of each dose of romidepsin in cycle 1 and cycle 2 the patients level of potassium (K+) and magnesium (Mg) must be confirmed to be greater than or equal to the lower limit of normal for the testing laboratory, or corrected to those levels. In cycle 3 and beyond, magnesium and potassium levels may be checked up to 3 days before romidepsin. If within treatment range they do not need to be repeated prior to romidepsin administration. Intravenous (IV) supplementation with potassium chloride (KCL) and/or magnesium sulfate can be used. If supplementation is necessary, documentation of levels after IV supplementation is required. Supplementation with oral KCL or magnesium oxide (MgOX) or magnesium soy (MgSoy) can be used. These parameters apply to both the phase lb and IIa portion of the study.

# 9.3 Treatment plan carfilzomib/romidepsin/lenalidomide Phase Ib

#### 9.3.1 Lead-in Dose

The initial dose of carfilzomib (cycle 1, day 1) given to any patient regardless of dose level must be 20mg/ m^2. All subsequent doses of carfilzomib will be based on the patient"s dose level.

#### 9.3.2 Dose Escalation

Subjects enrolled into the phase 1b portion will enroll at dosing level 1 with three patients per dosing level (3+3 design). A cycle will be 21-days. Based on toxicity

and activity seen during the phase lb portion, additional dose levels and/or alternate 28 day cycle may be explored through an amendment. The carfilzomib will be given intravenously weekly on days 1 and 8. The romidepsin will be given intravenously on days 1 and 8. The lenalidomide will be given as a once a day oral drug given on days 1-14. It is preferred that romidepsin be administered prior to carfilzomib.

TABLE 1: Phase I Dose Escalation			
Dose	Romidepsin	Lenalidomide	Carfilzomib
Level			(mg/m²)
-1	8 mg/m 	10 mg	20
1	8 mg/m 	15 mg	36
2	8 mg/m 	15 mg	45
3	10 mg/m 	20 mg	45
4	10 mg/m 	20mg	56
		J	

If all three patients complete one cycle of therapy without a DLT at the respective

- dose level then the subsequent dose level can be accrued.

  A DLT is defined in cycle 1 of the phase I portion as:

   Non-hematologic toxicity of grade ≥3 (attributed to study drugs with the exception of alopecia, nausea, or grade ≥3 vomiting not responsive to antiemetics)
  - Hematologic grade 4 toxicity (attributed to study drugs) defined as grade 4 thrombocytopenia of any duration; grade 4 neutropenia lasting more than 5 days; or grade 4 anemia unexplained by the underlying disease
  - Grade ≥3 thrombocytopenia with clinically significant bleeding
  - Febrile neutropenia of any duration (ANC <1.0K/ µL with fever 38.5°C)
  - Inability to receive day 1 of cycle 2 due to continued drug-related toxicity including Grade ≥ 2 toxicity that does not resolve to Grade ≤ 1 by the start of the next cycle.
  - Grade 3 thrombocytopenia or neutropenia (attributed to study drug) within cycle 1 that results in a) ≥ 4 day delay in any romidepsin or carfilzomib dose or b) missing greater than 4 days of lenalidomide. (This criteria only applies to the **phase lb portion** and does not apply to the phase Ila stopping rules).

After the MTD is determined by either DLT or accrual of six patients without DLT at dose level 4 in the first cycle accrual to the phase Ib portion will be considered closed. The MTD from the phase lb study will be used for the phase lla portion.

Of note, only patients who complete ≥80% of the doses of carfilzomib, romidepsin and lenalidomide during the first cycle will be evaluable for MTD. Patients who do

not meet this criteria for minimum drug exposure and do not have a dose limiting toxicity will be replaced for determination of MTD.

The treatment plan is described below for the **phase lb portion**:

- Romidepsin/Lenalidomide/Carfilzomib: Romidepsin IVPB over 4 hours on days 1 and 8
- Carfilzomib IVPB administered over approximately 30 minutes on days 1 and 8\*\*
- Lenalidomide PO q days 1-14

